9. SCREENING AND RANDOMIZATION

9.1. Screening

Subjects must provide informed consent before any screening tests are performed (Section 17.3). Participating study sites are required to document all screened candidates initially considered for inclusion in the study.

Screen failures are defined as subjects who sign the ICF but are not subsequently randomized or dosed. If a subject is considered a screen failure, the reasons for exclusion must be documented in the subject's source documents and on the screening log. A minimal set of screen failure information is required to ensure transparent reporting of screen failure participants to meet the Consolidated Standards of Reporting Trials publishing requirements and to respond to queries from regulatory authorities. Minimal information includes demography, screen failure details, eligibility criteria, and any SAEs.

Subjects with IPF who do not meet the criteria for participation in this study under Version 2 of the protocol may be rescreened one time only after discussion between the Principal Investigator and the Sponsor. Subjects with IPF who did not meet the criteria for participation in this study (i.e., a screen failure) under Version 1 of the protocol due to previously adapted ATS 2011 guidelines or hepatitis B criteria, may be screened and rescreened again under Version 2 of the protocol.

9.2. Randomization

Subjects will be randomized after all screening assessments have been completed and after the Investigator has verified that the subjects are eligible per criteria in Sections 8.1 and 8.2.

Subjects will be assigned a unique identification number that will be used on study-related documents pertaining to the subject. Any subject identification numbers that are assigned will not be reused even if the subject does not receive treatment or continue in the study.

Randomization will be performed using interactive response technology (IRT). Subjects will be randomized to receive BG00011 or placebo in a 1:1 ratio.

Refer to the Study Reference Guide for details on randomization.

9.3. Blinding Procedures

This is a randomized, double-blinded, placebo-controlled study.

All study staff will be blinded to the subject treatment assignments. To maintain the study blind, it is imperative that subject treatment assignments are not shared with the subjects, their families,

CONFIDENTIAL

The information contained herein may not be used, disclosed, or published without the written consent of
Biogen MA Inc.

or any member of the study team, either at the study site or at the Sponsor, except the unblinded Pharmacy staff and designated Sponsor personnel.

At the end of the study (i.e., once the clinical study report is finalized), if unblinding will not jeopardize the results of ongoing related studies, the Sponsor will provide the randomization codes to Investigators, who then can inform their subjects about the treatment received.

CONFIDENTIAL

The information contained herein may not be used, disclosed, or published without the written consent of Biogen MA Inc.

10. DISCONTINUATION OF STUDY TREATMENT AND WITHDRAWAL OF SUBJECTS FROM THE STUDY

10.1. Discontinuation of Study Treatment

Study treatment discontinuation is defined as the premature ending of study treatment dosing, i.e., when a subject permanently stops taking the study treatment before the last dose (the Week 51 dose). Reasons for mandatory study treatment discontinuation are listed in Section 10.1.1. The primary reason for study treatment discontinuation must be recorded in the subject's CRF.

Subjects who discontinue study treatment must return for an End of Treatment Visit as soon as possible, but within 4 weeks after discontinuation of treatment. All assessments planned for the Week 52 Visit except the HRCT scan will be performed. If the End of Treatment Visit occurs in the visit window for the next scheduled visit, then the scheduled visit may serve as the End of Treatment Visit, and all assessments for the End of Treatment Visit should occur at that time. Subjects will go on to complete all remaining visits as scheduled, including the Week 52 and Safety Follow-Up Visits (see Table 2 for a list of assessments to occur at the End of Treatment and Safety Follow-Up Visits).

Note: A subject who misses 1 or more doses of study treatment should restart study treatment, receive all remaining doses, and complete all remaining study visits.

See Section 10.2 for information related to the withdrawal of subjects from study.

10.1.1. Reasons for Study Treatment Discontinuation

A subject *must* permanently discontinue study treatment for any of the following reasons:

- The subject becomes pregnant. Study treatment must be discontinued immediately. Report the pregnancy according to the instructions in Section 15.4.1.
- The subject experiences an AE that necessitates permanent discontinuation of study treatment.
- If organ transplantation is planned to occur during the study treatment or Safety Follow-Up Period.
- The subject experiences an urgent medical event that necessitates unblinding of the subject's treatment assignment.
- The subject is unwilling or unable to comply with the protocol.
- At the discretion of the Investigator for medical reasons.

CONFIDENTIAL

The information contained herein may not be used, disclosed, or published without the written consent of Biogen MA Inc.

- The subject withdraws consent to continue study treatment.

10.1.1.1. Safety Criteria for Study Treatment Discontinuation

Liver Chemistry:

Liver chemistry threshold discontinuation criteria have been designed to ensure subject safety and to evaluate liver event etiology during administration of study treatment and during the Follow-Up Period. Study treatment will be discontinued if any of the following criteria are met:

- AST or ALT $\geq 3 \times$ ULN and total bilirubin level $\geq 2 \times$ ULN
- AST or ALT $\geq 5 \times$ ULN: study treatment will be discontinued if the result is confirmed upon retest within 48 hours.
- AST or ALT $\geq 3 \times$ ULN: study treatment will be discontinued if associated with the appearance or worsening of rash or hepatitis symptoms (i.e., fatigue, nausea, vomiting, right upper quadrant pain or tenderness, fever, rash or eosinophilia).

10.2. Withdrawal of Subjects From the Study

Study withdrawal is defined as the premature ending of study visits and assessments. The reasons for mandatory study withdrawal are listed below (Section 10.2.1). Note that discontinuation of study treatment does not require withdrawal from the study if a subject continues to attend clinic visits and complete assessments.

If a subject is withdrawn from the study, an End of Treatment Visit will be scheduled or performed as soon as possible but within 4 weeks. All assessments planned for the Week 52 Visit except the HRCT scan will be performed (see Table 2 for a list of assessments to occur at the End of Treatment Visit).

If a subject is unwilling or unable to attend, at minimum, the End of Treatment Visit, and decides to withdraw consent, the reason for withdrawal will be documented and no further assessments will be obtained.

Subjects who are withdrawn from the study will not be replaced.

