7.3. Study Stopping Rules

Biogen may terminate this study at any time. The Sponsor will notify Investigators if the study is to be placed on hold, completed, or terminated.

The DSMB will conduct regular reviews of all safety data in an unblinded format. Following each review, the DSMB will provide a recommendation to the Sponsor regarding the appropriateness of continuing the study from a safety perspective, as well as any other recommendations relevant to study conduct and/or subject safety.

The DSMB may recommend discontinuing the study if the event rate in the BG00011 treated arm is 20% higher compared with placebo. The events include, but may not be limited to:

- cumulative number of deaths and/or;
- number of lung transplantations and/or;
- cumulative number of subjects with a confirmed absolute decline of % predicted FVC ≥ 15 from baseline.

The meeting intervals and the procedures used to provide and assess the data will be described in detail in the DSMB charter.

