10.3. Lost to Follow-Up

Subjects will be considered lost to follow-up if they repeatedly fail to return for scheduled visits and are unable to be contacted by the study site.

The following actions must be taken if a subject fails to return to the clinic for a required study visit:

- The site must attempt to contact the subject and reschedule the missed visit as soon as possible and counsel the subject on the importance of maintaining the assigned visit schedule and ascertain whether the subject wishes to and/or should continue in the study.
- In cases in which the subject is deemed lost to follow-up, the investigator or designee must make every effort to regain contact with the subject. These contact attempts should be documented in the subject's medical record.
- If the subject continues to be unreachable, that subject will be considered to have withdrawn from the study with a primary reason of lost to follow-up.

CONFIDENTIAL

The information contained herein may not be used, disclosed, or published without the written consent of
Biogen MA Inc.

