15.3.2. Serious Adverse Events

Any SAE experienced by the subject between the time of the signing of the ICF and the subject's last study visit is to be recorded on an SAE form, regardless of the severity of the event or its relationship to study treatment. SAEs must be reported to the Sponsor within 24 hours as described in Section 15.3.3. Follow-up information regarding an SAE also must be reported within 24 hours. See the Study Reference Guide's Official Study Contact List for complete contact information.

Subjects will be followed for all SAEs until their last study visit. Thereafter, the event should be reported to the Sponsor only if the Investigator considers the SAE to be related to study treatment.

SAEs that are ongoing when the subject completes or discontinues the study will be followed by the Investigator until the event has resolved, stabilized, or returned to baseline status. SAE outcome will be recorded on the CRF, as applicable. Only SAEs that are unresolved will be followed by the Investigator.

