16.9. Sample Size Considerations

The sample size calculation is based on the annual declining rate in FVC (mL/year). With 145 subjects randomized per arm, and assuming a 15% dropout rate over a 1-year treatment period, the study has approximately 80% power to show that the BG00011 treatment arms differentiate from the arm without BG00011 at a 2-sided 15% α level, given a treatment effect of 82.5 mL/year with a common standard deviation of 280 mL. The calculation is based on the assumption that the FVC decline rate in subjects receiving placebo and no background therapy is 220 mL/year, and in subjects receiving background but no BG00011 therapy it is assumed to be 110 mL/year. A 60% reduction in the FVC decline rate in the subjects receiving placebo would be a treatment effect of 132 mL/year. A 30% reduction in the FVC decline rate in subjects receiving background therapy would be a treatment effect of 33 mL/year. With the assumption that 50% of each type of subject are randomized in the study, the combined treatment effect is approximately 82.5 mL/year. The 15% dropout rate for this study was estimated based on prior experience for the placebo arms in the Phase 3 studies for nintedanib and pirfenidone [King 2014; Richeldi 2014].

CONFIDENTIAL

The information contained herein may not be used, disclosed, or published without the written consent of Biogen MA Inc.

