7.3.3.2 Other Time-to-Event endpoints

The time-to-event types secondary efficacy endpoints listed as follows will be applied only by the Kaplan-Meier curve method where number of subjects at risk at each visit and the proportion of subjects who progressed in each treatment group will be summarized and presented.

- Time to first acute exacerbation (using modified diagnostic criteria for acute IPF exacerbation derived from [Collar 2007]), measured in days.
- Time to death or lung transplantation measured in days.
- Time to all nonelective hospitalizations, measured in days.
- Time to all nonelective respiratory hospitalizations, measured in days.

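### No vital or transplant status is sought after study withdrawal or loss to follow-up, so later deaths and transplants can be lost from time to death or transplantation, the progression composite and the DSMB counts

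*Protocol*

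**What the plan says.** **Withdrawal.** Protocol Section 10.2 defines study withdrawal as the early end of visits and assessments. A withdrawn subject is due one End of Treatment Visit within 4 weeks. If the subject cannot or will not attend even that visit and withdraws consent, "the reason for withdrawal will be documented and no further assessments will be obtained".

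**Loss to follow-up.** Section 10.3 requires documented attempts to regain contact. If these fail, "that subject will be considered to have withdrawn from the study with a primary reason of lost to follow-up".

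**Event reporting.** Section 15.3.2 follows SAEs while the subject is still attending and then narrows the duty: "Thereafter, the event should be reported to the Sponsor only if the Investigator considers the SAE to be related to study treatment". By exception, an SAE already ongoing when the subject leaves is followed to outcome regardless of relatedness. Section 15.3.3.1 requires all causes of death to be reported within 24 hours of site awareness, with no relatedness condition and no end date.

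**Use of the events.** SAP Section 7.3.3.2 lists "Time to death or lung transplantation measured in days" among the secondary endpoints, and the matching objective asks for transplant-free survival at Weeks 26 and 52. Death and transplantation are also components of the progression composite (SAP Section 7.3.3.1). The DSMB events in Protocol Section 7.3 include deaths ("cumulative number of deaths and/or") and transplantations.

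**Censoring.** SAP Section 7.3.3 censors a subject without an event at the last assessment in the treatment period. No sensitivity analysis for informative censoring is named.

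SAP Section 1 states that protocol Version 2 was not implemented. Version 1 has the same rules on withdrawal, loss, SAE reporting and deaths, so the point applies to both.

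**The concern.** Transplant-free survival at a fixed date needs each randomized subject's status at that date. Here, status is known only while the subject attends visits, or if the site happens to hear of an event. In a progressive, fatal disease, the reasons for leaving a study and the risk of dying may well be linked. Section 10.2.1 makes inability to comply a mandatory reason for withdrawal, which can include being too ill to attend. Section 14.1 lists study discontinuations due to urgent need for transplantation as something to track.

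If withdrawal carries prognostic information, censoring at the last assessment biases the Kaplan-Meier estimate in each arm. If withdrawal patterns also differ between arms, the comparison is biased. The effect goes beyond a descriptive curve: the SAP keeps a Cox model and a stratified log-rank test for the composite, and the DSMB compares arms on deaths and transplantations.

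**Working it through.** **1. The plan's own figure.** Protocol Section 16.9 gives the inputs: "With 145 subjects randomized per arm, and assuming a 15% dropout rate over a 1-year treatment period", and a test "at a 2-sided 15% α level, given a treatment effect of 82.5 mL/year with a common standard deviation of 280 mL". Subjects remaining per arm: 145 × 0.85 = 123.25. Power = Φ(82.5 / (280 × √(2/123.25)) − 1.4395) = Φ(2.313 − 1.4395) = 0.809. This agrees with the statement that "the study has approximately 80% power". The dropout figure is thus used in the sample size as stated, but it concerns FVC. No event rate, hazard ratio or power is given for death or transplantation, so step 3 is an illustration.

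**2. Which groups have later status recorded.**

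| Group | After leaving | Later death or transplant |
|---|---|---|
| Stops treatment only (10.1) | Completes all visits | Captured |
| Withdraws, attends End of Treatment Visit (10.2) | One visit within 4 weeks | No status check |
| Withdraws consent, does not attend (10.2) | Nothing | No status check |
| Lost (10.3) | Contact attempts | No status check |
| Leaves with an ongoing SAE (15.3.2) | SAE followed to outcome | Death from that SAE should be captured |

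For a new fatal event after the last visit, Section 15.3.2 asks for a report only if it is judged related; Section 15.3.3.1 asks for one whenever the site is aware. The text does not say which governs. For a new transplantation there is only Section 15.3.2.

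**3. Scale.** Leavers: 290 × 0.15 = 43.5. Stayers: 290 − 43.5 = 246.5. Assumptions, not in the documents: all leavers are true study withdrawals, alive on leaving; half a year is unobserved on average; the death or transplant hazard h is 0.07 to 0.198 a year; and leavers have 1 to 3 times that hazard (RR) after leaving. The upper h is ln 2 / 3.5 = 0.198, from the 3.5-year median survival in Protocol Section 4.1.

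- Missed events = 43.5 × (1 − exp(−h × RR × 0.5)).
- Stayers' events = 246.5 × (1 − exp(−h)).
- For the share, the denominator adds the leavers' first half-year events at hazard h, 43.5 × (1 − exp(−0.5h)), to the missed events and the stayers' events.

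| h | RR | Missed | Stayers' events | Leavers' earlier events | Share missed |
|---|---|---|---|---|---|
| 0.07 | 1 | 1.5 | 16.7 | 1.5 | 7.6% |
| 0.07 | 3 | 4.3 | 16.7 | 1.5 | 19% |
| 0.10 | 1 | 2.1 | 23.5 | 2.1 | 7.7% |
| 0.10 | 3 | 6.1 | 23.5 | 2.1 | 19% |
| 0.198 | 1 | 4.1 | 44.3 | 4.1 | 7.8% |
| 0.198 | 3 | 11.2 | 44.3 | 4.1 | 19% |

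**4. Cross-check.** Let leaving times be uniform over 52 weeks. Missed events are then 43.5 × [1 − (1 − exp(−k))/k], with k = RR × h. At annual risks of 5%, 10% and 18%, this gives 1.1, 2.2 and 4.0 events at RR = 1, and 3.2, 6.2 and 10.7 at RR = 3. As a share of missed plus stayers' events, this is about 8% to 20%. The scale is the same.

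**The case against.** Several limits on the point are real.

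- A reader might infer that later deaths are reported only if judged drug-related. The documents do not support that: Section 15.3.3.1 covers all causes of death once the site is aware, and SAEs ongoing at departure are followed. What stands is that awareness is left to chance, the two sections conflict for new fatal events, and transplantation has no equivalent rule.
- A reader might infer from the sentence in Section 10.2 that all data collection ends at withdrawal. It covers only those who withdraw consent without attending the End of Treatment Visit. Others have that visit, but nothing after it.
- A reader might infer that the lost events fall in the sickest subjects. Subjects who stop treatment for an adverse event, for medical reasons or for planned transplantation are meant to stay in follow-up (Sections 10.1 and 10.1.1). No document describes who withdraws. Informative withdrawal is plausible, not shown.
- A reader might link the gap to the trial's termination. SAP Section 1 says only that a prespecified safety composite was imbalanced. It does not name the components, and Protocol Section 7.3 also lists an FVC decline.
- The magnitude rests on assumed hazards. Section 16.9 does not define dropout as study withdrawal; if half the dropouts were true withdrawals, the range would be about 0.7 to 5.6 events. The upper hazard comes from IPF in general, whereas this trial enrols mild to moderate disease and excludes subjects likely to need transplantation within 12 months.
- After early termination, time to death or transplantation is analysed by Kaplan-Meier only. The composite keeps its formal tests.
- Consent pages were removed, and the Study Reference Guide, DSMB charter and Safety Monitoring Plan are not at hand. A status check specified there cannot be excluded.

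None of this supplies the missing check in the protocol or SAP.

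**Conclusion.** The point holds as a gap in ascertainment. Under the protocol and SAP as written, deaths and transplants after withdrawal or loss can go unrecorded, and subjects who have them are then censored as event-free. Whether this censoring is informative, and which arm it would favour, cannot be derived from the documents.

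The likely scale is about 1 to 11 events in 290 subjects, roughly 8% to 19% of all events. This is an upper bound for the assumed hazards: it treats every planned dropout as a living withdrawal and assumes that neither Section 15.3.2 nor Section 15.3.3.1 captures any event. The primary FVC power calculation is unaffected. The change is worth making because it is cheap and the endpoint cannot be fully observed without it.

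**What to change.** 1. **Protocol Sections 10.2 and 10.3.** For each withdrawn or lost subject, unless the subject refuses and where local law allows, record vital and transplant status at the planned Week 52 date, or at study close if earlier. Sources: phone contact, treating physician or public record.
2. **Protocol Sections 15.3.2 and 15.3.3.1.** Reconcile them so that any death or transplantation the site learns of is recorded regardless of relatedness, and reaches the DSMB counts.
3. **SAP Section 7.3.3.** For time to death or transplantation, count these dates as events; otherwise censor at the last known status date. For the composite, use them in a sensitivity analysis, because FVC decline is not observed after withdrawal and the components would otherwise have unequal follow-up.

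Cost: a consent sentence, one CRF page and about one contact for each of some 44 subjects, with no added visit or procedure. Downside: modest site time, and status will not be obtainable in every country or for subjects who refuse.

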10.2.1. Reasons for Withdrawal of Subjects from the Study

Subjects *must* be withdrawn from the study for any one of the following reasons:

- The subject withdraws consent.
- The subject enrolls into another interventional clinical study in which an investigational treatment or approved therapy for investigational use is administered.
- The subject is unwilling or unable to comply with the protocol.

CONFIDENTIAL

The information contained herein may not be used, disclosed, or published without the written consent of Biogen MA Inc.

10.3. Lost to Follow-Up

Subjects will be considered lost to follow-up if they repeatedly fail to return for scheduled visits and are unable to be contacted by the study site.

The following actions must be taken if a subject fails to return to the clinic for a required study visit:

- The site must attempt to contact the subject and reschedule the missed visit as soon as possible and counsel the subject on the importance of maintaining the assigned visit schedule and ascertain whether the subject wishes to and/or should continue in the study.
- In cases in which the subject is deemed lost to follow-up, the investigator or designee must make every effort to regain contact with the subject. These contact attempts should be documented in the subject's medical record.
- If the subject continues to be unreachable, that subject will be considered to have withdrawn from the study with a primary reason of lost to follow-up.

CONFIDENTIAL

The information contained herein may not be used, disclosed, or published without the written consent of
Biogen MA Inc.

11. STUDY TREATMENT USE

11.1. Regimen

Refer to and follow the Directions for Handling and Administration (DHA).

Approximately 290 subjects will be randomized into 2 dose groups as follows:

- Group 1: BG00011 56 mg by SC injection, once weekly for 52 weeks
- Group 2: Placebo by SC injection, once weekly for 52 weeks

The first dose of BG00011 or placebo (study treatment) will be administered at the study site during the Baseline Visit (Day 0). All subsequent doses should be administered by the subject or the subject's caregiver.

